#### **4.Design, procedures, materials and methods:**

Use a level of detail similar to what would be used when submitting an article for publication in a peer reviewed journal. Explain the study procedures, data collection, and analysis process. Please define terms and explain concepts which might be confusing to reviewers who are not expert in the area of the study. If a formal protocol for the study exists, page references to the protocol are acceptable.

Patient selection. Patients with medically refractory epilepsy are referred to DHMC for surgical evaluation. The first stage of the evaluation includes inpatient video EEG monitoring, epilepsy protocol MRI, and a neuropsychological evaluation. Following the initial evaluation, each patient's case is discussed in the epilepsy surgery conference. The conference is attended by all Dartmouth epilepsy neurologists and neurosurgeons. A consensus among all physicians is reached regarding further evaluation. Approximately 50% of patients require intracranial EEG (iEEG) recording prior to epilepsy surgery. If a patient requires iEEG, the strategy for the exact type of electrode implantation is determined at the same surgical conference. Subsequently, the need for iEEG monitoring is discussed with the patient in the outpatient clinic. Patients who meet clinical indication for iEEG recording will be asked to participate in the research study. If the patient agrees, certain standard electrodes will be substituted with the dual micro-macro electrodes during the iEEG recording.

Electrodes. Ad-tech is the largest manufacturer and supplier of intracranial electrodes for use in epilepsy surgery. Ad-tech standard macroelectrodes have been used at Dartmouth-Hitchcock Medical Center since 1992 in hundreds of iEEG cases. In addition to macroelectrodes, Ad-tech currently manufactures two types of dual macro-micro electrode systems that will be used in the study. The appropriate type of electrode system will be determined by the study team.

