One system is designed to mimic the original macroelectrode design with the addition of ultra-thin microelectrodes. The original macroelectrode dimensions and properties are retained and additional microelectrodes are positioned at the tip. Leads for the macro and micro electrode recording are separate and are connected to two distinct recording systems. Safety information for the use of the dual electrodes is provided from a single retrospective study of 24 patients who underwent the dual electrode implantation at Mayo Clinic. The complication rate for microelectrodes was 4% compared to 6% for standard electrode systems. Attachment #1 and Attachment #2 address the safety of the electrodes.

The second system (Behnke Fried/Micro Inner Wire Bundle) consists of an outer macro contact depth electrode that accepts delivery of an inner micro wire bundle. The micro contacts extend past the tip of the macro depth electrode.

Data Recording. Recording of iEEG using macroelectrodes has been routinely performed at Dartmouth using the Natus system. Recording of microelectrode potentials will be done using a separate Digital Lynx system or the clinical Natus system. The two systems are distinct and will not share information. The Digital Lynx system is a state-of-the-art microelectrode recording system manufactured by Neuralynx. Neuralynx provides the highest quality microelectrode recording equipment. The Digital Lynx system is not FDA approved for clinical use. However, it has been fully tested and meets the 60601 medical safety standards, has the 60601-1 safety certification for medical devices, and has meets the 60601-2-26 safety standards for EEG equipment. This system is available for clinical use through the lab of [name]. Attachment #3 addresses the safety of the Digital Lynx System.

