**Cognitive Tasks.** Patients who agree to participate in microelectrode studies may be asked to participate in a study which involves a cognitive task. Each task will be specifically designed to elicit a specific cognitive function important to testing of the regions where electrodes are implanted. The task could be a memory task, such as remembering of word pairs if electrodes reside in the hippocampus. The task may involve perception of facial emotion, mimicry of facial movements, mimicry of planned movements, smell appreciation, taste appreciation, appreciation of disgust, or visual spatial analysis. The type of task that a patient gets will depend on the region of the brain that is implanted by the microelectrode.

**Data Analysis.** Data on neuronal discharge characteristics will be recorded using the 64 Chanel Digital Lynx system running Cheetah software. The characteristics of fast ripples, and the data on neuronal firing characteristics during specific cognitive tasks will be exported to Matlab software for statistical analysis. Data analysis will be done by either the study team at DHMC/Dartmouth College, or by collaborators at Columbia University.

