**7. Statistical Methods and Review Statement:**

**a)** Specify the primary endpoint, as well as other endpoint(s).

The primary hypothesis is that high oscillations (fast ripples) occur in epileptogenic cortex and are absent in non-epileptogenic cortex. Our secondary hypothesis is that single unit activity recorded from various electrode positions in the brain will correlate with specific cognitive tasks.

**b)** State the statistical analysis plan, including all hypothesis tests (e.g., t-test, chi-square), and estimation methods related to the primary endpoint. If a formal protocol for the study exists, page references to the protocol are acceptable.

The recording of high frequency oscillations will require only basic statistical analysis using chi-square testing. The analysis of neuronal discharge characteristics and temporal association with specific cognitive tasks will be done using Matlab.

**c)** Justify the sample size, using the concepts of power, type I error, and effect size if applicable. If a formal protocol for the study exists, page references to the protocol are acceptable.

We are planning to enroll up to 50 patients over an extended period of time. The power calculations and effect size, will depend on the cognitive task applied in the individual patient for the specific electrode array.

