## **26. Privacy and Confidentiality:**

Describe the plans to protect the privacy of subjects and maintain the confidentiality of the data.

Note: Under certain circumstances, an invasion of privacy or breach of confidentiality may present a risk of serious harm to subjects (e.g., as when the research obtains information about subjects that would, if disclosed by the researcher, jeopardize jobs or lead to prosecution for criminal behavior). Under other circumstances, an invasion of privacy or breach of confidentiality can be a moral wrong

**a)** Will any study activities involve an interaction or reveal information for which protection of participant privacy is necessary?

- Yes
- No

If yes, please identify the activities and describe the plan to protect the privacy of participants. For example, a plan for protection of privacy might consist of conducting the assent process for an adolescent minor in a private setting, rather than in the presence of the minor's parent.

Data recorded during the study will include the names of patients, their dates of birth, medical record numbers, and results of testing. This information will be kept on DHMC servers. Data sent from DHMC to collaborators at Columbia University will be de-identified. Access to the data will only be available for investigators involved in the study.

De-identified EEG data collected for this study will be shared with other academic institutions, and added to public databases of EEG data. Data shared in this way will not include any identifying information.

**b)** Will the data collected in the course of the study be considered sensitive, e.g., include information about a mental health disorder, HIV status, or SS#?

- Yes
- No

If yes, provide the rationale for why these data are needed:

If yes, could any of these data, if disclosed, damage financial standing, employability, insurability, or reputation?

Yes  No

If yes, will a Certificate of Confidentiality be obtained?

Yes  No

Any person engaged in research collecting information about illegal conduct from human research subjects may apply for a Certificate of Confidentiality. NIH provides detailed instructions for investigators wishing to make an application at <http://grants.nih.gov/grants/policy/coc/index.htm>.

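### Fast-ripple scoring is not masked to site or tissue label, and the label need not be set without the microelectrode signal, so reading bias could produce the primary association

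*Combined protocol and SAP*

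**What the plan says.** Section 7a gives the primary hypothesis as "high oscillations (fast ripples) occur in epileptogenic cortex and are absent in non-epileptogenic cortex". Section 7b adds "The recording of high frequency oscillations will require only basic statistical analysis using chi-square testing". Neither part defines epileptogenic cortex, says who assigns that label, when or from what data, or gives a rule for calling a fast ripple present.

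On who analyses, Section 4 (Data Analysis) states "Data analysis will be done by either the study team at DHMC/Dartmouth College, or by collaborators at Columbia University". Section 26 adds "Data sent from DHMC to collaborators at Columbia University will be de-identified". Masking to electrode site or tissue label is mentioned in neither place.

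On where the signal is held, Section 4 (Data Recording) states "Recording of microelectrode potentials will be done using a separate Digital Lynx system or the clinical Natus system", followed by "The two systems are distinct and will not share information". The Data Analysis paragraph names only the Digital Lynx, for neuronal discharge data.

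On how the signal is used, the summary of Section 3 gives as the leading goal that microelectrode recording may help to identify epileptogenic cortex. Attachment G, item a, expects that microelectrode data have little chance of informing the participant's surgical decisions.

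**The concern.** The chi-square table crosses two judgements made at the same site. It tests the biology only if each judgement is made without knowledge of the other, and the plan secures neither.

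The more serious route is reading bias. A local analyst who knows which contacts lie in the suspected focus may call equivocal events differently there. The expectation is already set: Section 3 reports that fast ripples have been proposed as a marker found only in epileptogenic cortex. De-identification removes the patient's identity. It does not, as written, remove the electrode's location or its label.

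The lesser route is incorporation. If fast ripples help to decide which tissue is called epileptogenic, part of the association is true by construction. The plan leaves this open chiefly through the Natus option, since the stated separation of systems protects the label only when the research system is used.

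Both routes favour the hypothesis. The chi-square test can neither detect nor correct them, and enrolling more patients does not dilute them.

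**Working it through.** **No figure of the plan to reproduce.** Section 7c plans up to 50 patients and gives no type I error, power, effect size or fast-ripple rate for the primary endpoint. No number of sites is stated. The point rests on the text; the arithmetic shows only possible scale.

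**Assumed inputs.** No true association; fast-ripple rate p = 0.30 in both tissue classes (varied below from 0.20 to 0.50); n independent sites per label, n = 25, 50 or 100; two-sided 5% Pearson chi-square without continuity correction.

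**Reading bias.** A reader aware of the label calls fast ripples at rate p + s in sites labelled epileptogenic and p - s in the others. The test rejects when (x1/n - x2/n)^2 / [m(1 - m)(2/n)] > 3.84, where x1 and x2 are the counts of positive sites and m = (x1 + x2)/(2n). The rejection probability is the sum of the two binomial probabilities over all rejecting pairs (x1, x2).

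| Sites per label | s = 0 | s = 5 points (35% v 25%) | s = 10 points (40% v 20%) |
|---|---|---|---|
| 25 | 5.4% | 12.6% | 35.2% |
| 50 | 5.0% | 19.2% | 59.5% |
| 100 | 5.1% | 34.2% | 88.0% |

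Hand check at n = 50, s = 0.05, by the normal approximation:
- Null standard error: sqrt(2 x 0.30 x 0.70 / 50) = 0.0917.
- Standard error under the shift: sqrt[(0.35 x 0.65 + 0.25 x 0.75) / 50] = 0.0911.
- z = (0.10 - 1.96 x 0.0917) / 0.0911 = -0.87, so the probability is about 0.19, in line with 19.2%.

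Varying p from 0.20 to 0.50 at 50 sites per label gives 18-24% for +/-5 points and 54-73% for +/-10 points.

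**Incorporation.** Half of all sites start labelled epileptogenic, independently of fast ripples. A share q of the fast-ripple-positive sites labelled non-epileptogenic is then relabelled epileptogenic. With p = 0.30 and q = 0.20:
- Labelled epileptogenic: 0.30 x (0.5 + 0.5 x 0.2) = 0.18 positive, plus 0.70 x 0.5 = 0.35 negative, total 0.53. Apparent rate 0.18/0.53 = 34.0%.
- Labelled non-epileptogenic: 0.30 x 0.5 x 0.8 = 0.12 positive of 0.47. Apparent rate 25.5%.
- Rejection probability with 100 sites in all: 15%.

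For p from 0.20 to 0.50 and 100 sites in all, q = 10%, 20% and 30% give 7-9%, 12-17% and 22-33%. With 400 sites in all they give 13-17%, 36-52% and 68-86%.

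**Statements that do not sit together.** Data Recording allows either recorder, while Data Analysis names one. Section 3 hopes that the signal helps to identify epileptogenic cortex, while Attachment G expects it to have little bearing on surgical decisions. Each pair needs reconciling, because the answers determine whether incorporation can arise.

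**The case against.** **Overlap of people is inferred.** A reader might infer that the local team which localises the focus also labels the research sites, citing Section 4: "The conference is attended by all Dartmouth epilepsy neurologists and neurosurgeons". That does not follow. The conference takes place before implantation; it decides whether intracranial recording is needed and how to implant. It labels no microelectrode site and cannot have seen microelectrode data. This objection stands: the documents name no labeller and simply do not exclude overlap.

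**Visibility on Natus is inferred.** A reader might also infer that fast ripples are in view whenever Natus records the microelectrodes. Section 3 places them at 80 to 1000 Hz, and no sampling, filter or display setting is given, nor any statement that clinical readers review those channels. This stands too.

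**Safeguards exist.** The systems are said not to share information, one electrode type has its macro and micro leads going to distinct systems, and Attachment G expects little influence on surgery. These lower the weight on incorporation. They do not remove it, since the Natus option bypasses the separation and an expectation about surgery is not a rule about the research label. They do nothing for reading bias. The Columbia route could supply independence, but it is optional and not stated to be masked.

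**The sizes are assumed.** A +/-10-point shift is a 20-point gap from reading alone, and the results depend heavily on site count. Correlation between sites within a patient is left out. All fair, so the figures cannot be read as estimates.

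**The definitions come first.** Epileptogenic cortex, the detection rule and the unit of analysis are all unspecified, and a fixed automated detector would remove much of the reading bias. This supports the fix, which calls for a recorded label and a fixed detector.

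**Conclusion.** The concern holds as a statement about what the plan permits: unmasked local scoring of fast ripples, against a label that need not be independent of the microelectrode signal. Reading bias is the main weakness; incorporation is secondary and conditional, chiefly on use of Natus. The documents do not show that the same people make both judgements, that the label will be drawn from fast ripples, or that bias of any particular size will occur.

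Under the stated assumptions, a modest label-linked shift of +/-5 points would raise a nominal 5% error rate to roughly 13-34% over 25 to 100 sites per label. That is enough to leave a significant primary result open to a second explanation. The protection is cheap and cannot be restored for a reader who has seen both readings, so the plan should be changed rather than the matter left to reporting.

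**What to change.** In Section 4, Data Analysis, add two rules.

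1. Record and lock the research tissue label of each microelectrode site from the clinical and macroelectrode data, without the microelectrode signal, before any microelectrode signal is reviewed for research. This applies equally when Natus is the recorder. State who sets the label.
2. At export, replace patient, channel and region names with random codes, run one fixed detector setting on all channels, and lock the fast-ripple table before the codes are opened. The existing export to Columbia can serve as the coded route.

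Also reconcile the recorder named in Data Recording with that in Data Analysis, and the goal in Section 3 with the expectation in Attachment G.

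The label in rule 1 is for research only and changes no clinical care. The cost is a renaming step and locked label and fast-ripple records for each patient. An existing team member must hold the code key, artefact queries pass through that person, and scoring waits for the label. No additional reader is needed.

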### **5. Inclusion/Exclusion Criteria:**

Please provide detailed description of inclusion and exclusion criteria. If a formal protocol for the study exists, page references to the protocol are acceptable.

Inclusion criteria:

1. 18-65 year old
2. male or female
3. right or left handed
4. IQ>70
5. medically refractory focal epilepsy requiring intracranial EEG for pre-surgical evaluation deemed medically necessary
6. no contraindications to intracranial electrode study
7. able and willing to participate in research

Exclusion criteria:

1. does not meet the inclusion criteria

### **6. Financial Considerations:**

Disclosure of financial impact on the participant is critical to informed consent. Insurance cannot be billed for research-related services outside the standard of care or paid for by the funding agency for the study. The department, the study or the participant may be responsible for payment for research-related services. Participants should know which tests, visits, or procedures will be billed to them or their insurance and which ones will be paid by the funding agency for the study or the department.

**a)** List tests, visits, and procedures performed for only research purposes. These services are outside the standard of care. They would not be performed if the individual were not a research participant, and may not be billed to a health insurance plan.

Note: 6a information must also be in "How is this different . . ." section of the consent form.

There is no predicted extra cost to the patient if they choose to participate in the study. We will purchase the research portion of the dual micro-macro electrode system using research funds. Use of Digital Lynx system, collection of data, data analysis, creating and administration of neurocognitive tasks will be done during research time of individuals in the study. Nothing that is done outside the standard of care will be billed to the patients.

**b)** List the tests, visits, and procedures that may be standard care, but for which the funding agency for the study is paying.

None

**c)** Will the funding agency for the study be responsible for the above costs?

Yes  No

If No, describe who will be responsible (i.e., department or participant).

The Department of Neurology will be responsible for all research costs outside of standard of care.

**PLEASE ENCLOSE THE DHMC BILLING GRID/PLAN. Also enclose the schedule of events or table listing all procedures from the sponsor protocol. A Billing Grid will not be applicable to this study as there is not a sponsor and all procedures are standard of care. There are only 2 points of contact with the patient regarding the study: 1. Consenting the patient after a routine office visit and 2. Standard of care surgical evaluation.**

**7. Statistical Methods and Review Statement:**

**a)** Specify the primary endpoint, as well as other endpoint(s).

The primary hypothesis is that high oscillations (fast ripples) occur in epileptogenic cortex and are absent in non-epileptogenic cortex. Our secondary hypothesis is that single unit activity recorded from various electrode positions in the brain will correlate with specific cognitive tasks.

**b)** State the statistical analysis plan, including all hypothesis tests (e.g., t-test, chi-square), and estimation methods related to the primary endpoint. If a formal protocol for the study exists, page references to the protocol are acceptable.

The recording of high frequency oscillations will require only basic statistical analysis using chi-square testing. The analysis of neuronal discharge characteristics and temporal association with specific cognitive tasks will be done using Matlab.

**c)** Justify the sample size, using the concepts of power, type I error, and effect size if applicable. If a formal protocol for the study exists, page references to the protocol are acceptable.

We are planning to enroll up to 50 patients over an extended period of time. The power calculations and effect size, will depend on the cognitive task applied in the individual patient for the specific electrode array.

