## **12. Timetables:**

**a)** Indicate length of participant involvement in the study: **Each participant will be enrolled into the study for the duration of their iEEG monitoring, this is an inpatient admission of less than two weeks.**

**b)** Estimate how long it will take to enroll enough participants to complete this study: **This will be an ongoing study. We think we can enroll 2-3 patients per year.**

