**16. Adequacy of Resources to Protect Subjects:**

**a)** Investigator (including co-investigators) has sufficient time to conduct and complete the research.

Yes  No

**b)** Adequately qualified (including experience, training, supervision, and familiarity with the protocol) staff are available for this research.

Yes  No.

**c)** Describe availability of psychological, social, or medical services, which include counseling or social support services, that may be required as a consequence of research participation.

Patients are routinely evaluated by neuropsychologists as part of routine work-up. As subjects will be inpatients during their participation in the study, epilepsy, neuropsychiatry, and psychology services will be available.

**d)** Describe psychological, social, or medical monitoring, ancillary care, equipment needed to protect participants (e.g. close proximity to resuscitation equipment or a plan for monitoring of emotional state during study procedures).

The study will be conducted inside the Epilepsy Monitoring Unit (EMU) at DHMC. This unit is specifically equipped to deal with complications of epilepsy and epilepsy surgery. The unit has continuous video EEG monitoring, meets safety standards for operating an EMU, has specially trained and qualified nurses who are able to treat seizures.

e) Describe other resources needed for the protection of subjects in the conduct of this research (e.g. language translation services).

None

**f)** Explain how the investigator has access to a population that would allow recruitment of the required number of subjects.

Patients who have medically refractory epilepsy are referred to the DHMC Epilepsy Center for surgical evaluation. Each year, between 10-15 intracranial EEG studies are performed. Patients will be recruited from among all patient who meet the inclusion criteria. We anticipate that 5-8 patients per year will be recruited to participate in the study.

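### The primary hypothesis says fast ripples are absent from non-epileptogenic cortex, but the only named analysis is a chi-square test, which can show a difference and not absence

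*Combined protocol and SAP*

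**What the plan says.** All of the primary analysis is in section 7 (Statistical Methods and Review Statement).

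- Item a, hypothesis: "The primary hypothesis is that high oscillations (fast ripples) occur in epileptogenic cortex and are absent in non-epileptogenic cortex".
- Item b, analysis: "The recording of high frequency oscillations will require only basic statistical analysis using chi-square testing". The form's prompt for this item also asks for estimation methods for the primary endpoint. The answer gives none.
- Item c, size: "We are planning to enroll up to 50 patients over an extended period of time". Power and effect size are tied there to the cognitive tasks, not to fast ripples.

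The Data Analysis paragraph of section 4 names a program and no method: "The characteristics of fast ripples, and the data on neuronal firing characteristics during specific cognitive tasks will be exported to Matlab software for statistical analysis".

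No section gives a confidence interval, an upper bound, a tolerated rate or a decision rule for absence. The unit of the chi-square table (patient, electrode, bundle or microwire) is not named either. On layout, section 4 says that "certain standard electrodes will be substituted with the dual micro-macro electrodes during the iEEG recording", and it describes one of the two systems as carrying a bundle of microwires at a single location.

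**The concern.** The hypothesis has two halves: fast ripples occur in one tissue class, and they do not occur in the other. A chi-square test of presence against class has equal proportions as its null, so rejection supports only the statement that the proportions differ. The table's counts could refute absence, because one verified positive is enough. Zero or few positives do not establish it without a statement of how large the true proportion could still be.

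The second half matters scientifically. The Introduction reports that fast ripples have been put forward as a marker found only in epileptogenic tissue, and its summary ranks finding such tissue as the leading goal. How often fast ripples appear in other tissue is the quantity on which that idea depends, and the plan does not say it will estimate it. Followed as written, the plan could attach a very small p-value to a conclusion that the p-value does not support.

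A second matter affects the same test. If several sites per patient are entered, a plain chi-square treats them as independent.

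**Working it through.** **Inputs from the documents.** The absence hypothesis and chi-square testing (section 7a and 7b), and a cap of 50 patients (section 7c). The figure of 50 cannot be reproduced, because no alpha, power, rates or effect size for fast ripples are given. All counts, rates, sites per patient and intraclass correlations (ICC) below are assumptions for illustration.

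**1. The test rejects when absence is plainly false.** Assume 50 independent observations per class, with 40/50 positive in epileptogenic and 20/50 in non-epileptogenic cortex.

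- Chi-square (no continuity correction) = 100 × (40×30 − 10×20)² / (50×50×60×40) = 16.7, p = 0.00004. With correction, p = 0.0001.
- The non-epileptogenic proportion is 40% (exact 95% CI 26% to 55%).
- With true rates of 80% and 40%, power to reject at two-sided 5% is 99%.

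**2. When the data do look like absence, the p-value does not size what remains possible.** Assume 15/20 against 0/20.

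- Chi-square = 40 × (15×20 − 5×0)² / (20×20×15×25) = 24.0, p about 0.000001.
- The exact one-sided 95% upper bound for 0/20 is 1 − 0.05^(1/20) = 13.9%.

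**3. What the cap allows if the patient is the unit.** The quantity is the share of patients with any positive non-epileptogenic site. With zero positive patients the bound is 1 − 0.05^(1/n).

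| Patients with a non-epileptogenic site | Upper bound, zero positive |
|---|---|
| 20 | 13.9% |
| 29 | 9.8% |
| 50 | 5.8% |
| 59 | 4.95% |

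A bound below 10% needs 29 patients with none positive, or 46 with one. A bound below 5% needs 59 with none positive, which exceeds the cap.

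**4. A site-level bound could be tighter.** Assume 50 patients with 4 non-epileptogenic sites each, so 200 sites, all negative. The design effect is 1 + 3×ICC: 1.6 at ICC 0.2 and 2.5 at ICC 0.5. Effective numbers are 200/1.6 = 125 and 200/2.5 = 80. The bounds are 1 − 0.05^(1/125) = 2.4% and 1 − 0.05^(1/80) = 3.7%. These are rough, since an ICC cannot be estimated from all-zero data.

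**5. Clustering, as illustration only.** Assume 4 sites per patient, no true difference and a nominal 5% test.

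- Classes in different patients: 2 × (1 − Φ(1.96/√1.6)) = 12.1% at ICC 0.2, and 2 × (1 − Φ(1.96/√2.5)) = 21.5% at ICC 0.5.
- Two sites of each class in every patient with a shared patient effect, variance factor 1 − ICC: 2 × (1 − Φ(1.96/√0.8)) = 2.8%, and 2 × (1 − Φ(1.96/√0.5)) = 0.6%.

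The error goes in opposite directions, and the documents do not give the layout.

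**6. The replacement test must permute the right unit.** Microwires of one bundle share a location and a class, so they are not exchangeable one by one. In a simulation with no true difference (assumed 50 patients, one bundle per class, prevalence 0.3, bundle ICC 0.2 to 0.5), permuting single wires within a patient gave a type I error of 13–26% with 4 wires per bundle and 20–39% with 8.

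**The case against.** The best reply is that this is mostly wording. Absence is asserted once, in the hypothesis line of an ethics application. The Objectives and the Introduction's summary are softer, exclusivity is reported only as a proposal by others, and nowhere does the plan commit to declaring absence. That stands as a limit on the size of the problem: if no such claim is intended, one reworded sentence settles it. It does not remove the point, because the document itself labels this hypothesis primary and the form asked for estimation methods.

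It can also be said that the table will contain the counts from which anyone can compute a bound. That is true. The data are not missing; the planned interval and rule are. A limit chosen after the counts are seen would carry little weight.

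Two stronger readings are tempting, and the documents support neither.

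- A reader might infer that 50 patients can never bound the rate below 5%. That holds only for the share of patients with any positive site. The hypothesis concerns cortex, and step 4 shows that a site-level bound could fall below 5%.
- A reader might infer that clustering inflates the false-positive rate. Step 5 shows that it could equally make the test conservative, and neither the unit nor the layout is stated.

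**Conclusion.** The point holds. The primary hypothesis includes absence, the only named test addresses difference, and no interval, bound or decision rule fills the gap. This is a matter of logic and does not rest on the assumed counts.

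The one size that uses a documented figure is the patient-level bound at the cap: 5.8% with none of 50 patients positive, provided every patient has at least one non-epileptogenic site. With 20 such patients it is 13.9%. A 5% patient-level limit therefore cannot be met within the cap, while a 10% limit can. The clustering figures only show that the unit and layout need stating; they do not estimate this study's error rate. The plan should be changed, but the change is small, and the whole matter shrinks to one sentence if absence will not be claimed.

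**What to change.** In sections 7a and 7b:

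1. State the tested hypothesis as fast ripples being more frequent in epileptogenic than in non-epileptogenic cortex.
2. Replace the plain chi-square with a within-patient permutation test, or another test that allows for clustering by patient. The permuted unit is the independently implanted electrode or bundle, with the microwires of one bundle collapsed to one value. State that patients with only one cortex class do not contribute to the within-patient test, which can happen because only some electrodes are replaced.
3. Report the proportion of non-epileptogenic sites with fast ripples, with a patient-clustered confidence interval. Also report the share of patients with any positive non-epileptogenic site, among patients who have such a site, with an exact one-sided 95% upper bound. Name which of the two quantities supports any absence or exclusivity claim, and make that claim only if its bound is below a limit fixed before analysis. If every site is negative, an ordinary clustered interval cannot be estimated reliably and the exact patient-level bound is the one to use.

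If no absence claim will be made, step 1 removes the mismatch and no limit is needed.

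The cost is about one paragraph, the choice of a limit, and slightly more analysis of the same recordings, with no added patients or procedures. The claim becomes less absolute, and the patient-level bound is conservative for the patient-averaged site proportion. Both the test and the bound also need stated rules for classing cortex and for detecting fast ripples, which is a separate matter.
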